SD	Standard deviation
SLIPS	Specific Loss of Interest and Pleasure Scale (SLIPS)
TEPS	Temporal Experience of Pleasure Scale
V0	Visit 0 (baseline)
V5	Visit 5 (primary outcome assessment at week 5 post-randomization)
VS	Ventral striatum
WHODAS	WHO Disability Assessment Schedule
WHO	World Health Organization

PURPOSE OF STATISTICAL ANALYTICAL PLAN (SAP)

The purpose of this SAP is to outline the planned analyses to be completed for the EZOR61-01 trial. The planned analyses identified in this SAP will be included in abstracts and manuscripts reporting the results of the trial. Exploratory analyses not necessarily identified in this SAP may also be performed. Any post hoc, or unplanned, analyses not explicitly identified in this SAP will be clearly identified as such in any published papers from this study.

1. INTRODUCTION

Depressive disorders are among the most disabling medical conditions worldwide and currently available treatments fall short of addressing this large public health burden. Dysfunction within the brain reward system is emerging as a core feature of depressive disorders, in particular related to deficits in motivation, interest, and response to pleasure (e.g., anhedonia: markedly diminished response to pleasure). Evidence from a series of preclinical studies highlighted the KCNQ subtype of neuronal potassium (K⁺) channel as a novel target for the treatment of depressive disorders, and data from human pilot study showed a reduction in anhedonia and related symptoms with an increased brain response to reward (as measured by functional magnetic resonance imaging [fMRI]) following treatment with ezogabine, a KCNQ channel opener. Building on these data, this study will assess reward circuit activity following treatment with ezogabine in depressed patients with anhedonia and will examine the relationship between change in reward circuit activity and clinically relevant symptom and behavior outcomes.

1.1 Study Objectives

1.1.1 Primary Objective

The primary objective of this study is to establish target engagement of a KCNQ channel opener (ezogabine) in patients with depressive disorder and anhedonia.

1.1.2 Secondary Objectives

Secondary objectives of this study are to determine if treatment with ezogabine is associated with a reduction in clinical symptoms of depression and anhedonia and with a modulation of behavioral responses to reward.

1.2 Study Design

This study is a Phase IIa, prospective, multi-site, randomized (1:1), parallel arm, double-blind, placebo-controlled clinical trial.

1.2.1 Study duration and time points

Participants will be followed for up to 14 weeks. The screening period may last up to 6 weeks; after randomization, titration and treatment lasts 5 weeks at which point the primary endpoint is ascertained. Participants will continue to be followed for a 3 week medication taper period after collection of the primary endpoint.

1.2.2 Randomization and masking

Patients will be randomized in a 1:1 allocation to ezogabine or placebo. Randomization will be stratified by center balanced by randomly permuted blocks, and treatment code will be allocated through the interactive web response system (IWRS). Randomization will take place only after it has been determined that all study eligibility criteria have been met and the baseline fMRI scan has been obtained.

This is a double-blind, placebo-controlled trial. Site personnel and patients will be blinded to treatment assignment throughout the trial.

2. STUDY POPULATIONS

Intent-to-Treat (ITT) Population

The ITT population is defined as all randomized subjects, regardless of when they withdrew from the study or received the assigned treatment. The ITT population will be used to present all data (including the primary endpoint) by randomized treatment group. Subjects will be analyzed according to the treatment to which they were randomized, regardless of the treatment they actually received.

3. EFFICACY ENDPOINTS

3.1 Primary Endpoint

The primary endpoint of this study is the baseline-corrected fMRI activation in an a priori bilateral ventral striatum (VS) area mask during the “gain” cue of the Incentive Flanker Task (IFT) contrasted with neutral cue for reward anticipation. The primary outcome fMRI will be obtained at 5 weeks post-randomization. The primary endpoint will be used as the sole criterion for the “go-no go” decision.

3.2 Secondary Endpoints

Secondary endpoints are measured at 5 weeks post-randomization unless otherwise noted. The following secondary endpoints will be analyzed. All secondary analyses will be considered exploratory and will not influence the study “go-no/go” decision.

3.2.1 fMRI Activation within the Reward Circuit

In the same manner as the primary endpoint, fMRI activation in other regions of the reward cortico-striatal circuit (medial prefrontal cortex [mPFC], bilateral dorsal striatum [DS], and anterior cingulate cortex [ACC]), as well as whole-brain analyses, will be measured during the gain cue of the IFT and contrasted with neutral cue.

Similarly, activation during the loss cues of the IFT task will be compared with the fMRI activation in neutral tasks.

3.2.2 Change in Anhedonia

Symptoms of anhedonia will be measured with the Snaith-Hamilton Pleasure Scale (SHAPS), the Temporal Experience of Pleasure Scale (TEPS), the Anticipatory and Consummatory Interpersonal Pleasure Scale (ACIPS), and the Specific Loss of Interest and Pleasure Scale (SLIPS). The SHAPS, TEPS, ACIPS, and SLIPS will be collected at baseline and weekly through the primary outcome assessment (V0 – V5).

3.2.3 Change in Depressive Symptoms

Symptoms of depression will be measured with the Quick Inventory of Depressive Symptomatology, Self-Report (QIDS-SR), the Montgomery-Asberg Depression Rating Scale (MADRS), the Mood and Anxiety Symptoms Questionnaire (MASQ),

and the Columbia-Suicide Severity Rating Scale (C-SSRS). The QIDS, MADRS, and C-SSRS will be collected at baseline (V0) and weekly through the primary outcome assessment (V1 – V5). The MASQ will be collected at baseline (V0) and primary outcome assessment (V5) only.

3.2.4 General Functioning

The Clinical Global Impression – Improvement and Clinical Global Impression – Severity scales will be used to measure overall illness severity at baseline and weekly through the primary outcome assessment (V0 – V5).

The World Health Organization (WHO) Disability Assessment Schedule 2.0 (WHODAS 2.0) will also measure general functioning. The WHODAS will be measured at baseline (V0) and at the time of the primary outcome assessment (V5).

3.2.5 Reward learning

The Probabilistic Reward Task (PRT) will be used as a behavioral assessment to calculate an index of reward learning at baseline (V0) and at the time of the primary outcome assessment (V5).

4. SAFETY ENDPOINTS

The incidence and frequency of all anticipated and unanticipated serious and non-serious adverse events (AEs) that occur between randomization and study exit (V8) eight weeks after randomization will be determined. Severity/grade and expectedness will be assessed by the study clinician. The Medical Dictionary for Regulatory Activities (MedDRA) system organ class and preferred terms will be recorded for each reported AE.

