8.4.1 Dosage/Dosage Regimen

Titration Period. Study drug titration will follow the guidelines contained within the FDA package insert and will not exceed the maximum approved dose for partial-onset seizures (1,200 mg daily). For this study, a daily dose of 900 mg has been selected, along with placebo.

For the ezogabine arm, participants start at 100 mg 3 times daily (300 mg per day) and increase at weekly intervals by 150 mg (50 mg 3 times per day) up to a stable dosage of 900 mg daily. A 150 mg increase each week is the maximum increase recommended by the FDA. Those assigned to receive placebo will receive capsules containing an inactive compound at a frequency comparable to those in active treatment (i.e., 1 capsule, 3 times per day). Dose titration will be conducted based on subject tolerability.

Subjects who are unable to tolerate a protocol-specified dose increase will be retained in the study at the highest tolerated dose for that subject through to the Primary Outcome Visit (V5), before beginning to taper off of the medication. In the event that a subject experiences a potential dose-dependent adverse medication effect in the opinion of the investigator, the subject will be maintained at the subject's highest previously tolerated dose. One dose reduction for the purpose of resolving suspected medication-related adverse effects will be allowed per subject. Subjects who continue to experience tolerability issues despite the dose reduction will initiate the taper phase and will be exited early from the study protocol. The taper schedule will follow procedures reported in section 10.5 "Taper Period" and section 10.6 "Study Exit Visit" (Visit 6) and early withdrawal". All available data for each subject will be included in the statistical analyses, including from subjects who discontinue early for any reason. Study subjects who discontinue early for any reason, however, will not be replaced. During the trial, the following dosages of ezogabine will be used: 50 mg, 200 mg and 300 mg. To assure the blindness of the trial, the research pharmacist at each site will encapsulate every pill so that all study pills regardless of dosage will look identical.

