10 EVALUATIONS BY VISIT

Study visits may occur within 3 days before or after the scheduled visit, except for V5 (Primary outcome visit), which may occur at any point after participants have been on their highest tolerated treatment dose from at least one week (7 days) up to a maximum of two weeks (14 days), and V8 which may take place within six weeks of the Primary Outcome Visit (V5). Please refer to Table 2 “Schedule of Assessments, Outcome Measures, Labs, and Procedures.”

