** The weekly phone calls during taper period (i.e. Visit 6 and Visit 7) will be conducted by a study research coordinator. The weekly phone calls will be scheduled one and two weeks after the Primary outcome visit (Visit 5), respectively. However, to ensure feasibility of the study and participants' availability, weekly phone calls may occur within 3 days before or after the scheduled one. If patients follow a one- or two-week taper period, one or two weekly phone calls will be scheduled respectively. An explicit request by the study participants or any safety concern (e.g., new and unexpected adverse effects, increased suicidality risk) will trigger a follow up phone call assessment by a study physician. At physician's discretion, an in-person visit will be scheduled.*

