10.6 Study exit Visit (Visit 6) and early withdrawal

1. Perform a clinical interview and history interval
2. Record any AEs.
3. Record changes to concomitant medications and review subject diary for adverse experiences and dosing compliance.
4. Perform a physical examination with recording of vital signs
5. Perform EKG.
6. Perform an ophthalmological exam.
7. Collect blood for clinical laboratory tests
8. Collect urine for urinalysis, urine toxicology and pregnancy test (applies to women of child-bearing potential only).
9. Perform self and clinician administered ratings scale:
 - SHAPS
 - TEPS

- ACIPS
- SLIPS
- QIDS-SR
- MADRS
- CSSRS
- CGI-S
- CGI-I

10. PRT*.

11. Structural MRI, fMRI during IFT, resting state connectivity*

Note: The exit visit may occur on up to three separate days, within 6 weeks of the Primary Outcome Visit (Visit 5). The subject will be considered exited from the study when all the procedures listed above will be completed.

** This procedure will be performed ONLY for early withdrawal visits that take place before completion of the primary outcome visit. Capturing outcome data for patients who do not complete the full study protocol will allow a more precise estimate of the treatment effect.*

Provision of study follow-up for treatment emergent adverse events at study exit: in case of any adverse event (including, but not limited to suicidal ideation or behavior) present at the study exit visit, subject will be referred to follow-up care until the event is resolved and/or a stable care plan is in place. The site PI will follow up with the subject until the abnormal parameter or symptom has resolved or stabilized.

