11.2 Serious Adverse Events (SAE)

An SAE is defined as any AE occurring at any dose that results in any of the following outcomes:

- Death
- Life threatening experience defined as any adverse experience that places the subject, in the view of the treating physician, at immediate risk of death at the time of occurrence; i.e, it does not include a reaction that, had it occurred in a more severe form, might have caused death.
- Requires inpatient hospitalization or prolongation of an existing hospitalization (except scheduled hospitalizations for non-acute, unrelated cause such as an elective surgery)
- Results in persistent or significant disability/incapacity
- Is a congenital anomaly/birth defect in the offspring of an exposed subject
- Important medical events that may not result in death, be life threatening, or require hospitalization, may be considered an SAE when, based upon appropriate medical judgment, it jeopardizes the subject and may require medical or surgical intervention to prevent one of the outcomes listed in this definition.
- Any death occurring within 30 days of the subject receiving study drug, regardless of the subject having discontinued from the protocol, must be reported as an SAE.

Other important medical events may also be considered an SAE when, based on appropriate medical judgment, they jeopardize the subject or require intervention to prevent one of the outcomes listed.

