11.2.1 AE/SAE Reporting Procedures

To local PPHS (IRB) and Sponsor (e.g., Study PI, [name])

AEs are reportable to the IRB and to the Study PI ([name]) within 5 business days *when they meet the following definition:*

Any harm experienced by a subject or other individual that in the opinion of the investigator is *unexpected AND at least probably related* to the research

A harm is *at least probably related* to the research if in the opinion of the investigator the research procedures more likely than not caused the harm

All AE/SAEs with an onset date after the subject signs consent for study participation must be reported to the IRB at the time of annual renewal. Details of the event must include severity, relationship to study drug, duration, action taken, and outcome.

All AE/SAEs that are considered related to study drug must be followed to resolution or stabilization if improvement is not expected. AE/SAEs that completely resolve and then recur should be recorded as a new AE/SAE. AE/SAEs that are considered related to study drug and continuing at 30 days post-last dose should have a comment in the source documents by the site PI that the event has stabilized or is not expected to improve.

To NIMH DSMB

All AEs and SAEs will be reported to the NIMH DSMB in data reports prepared three times annually. Details of the event must include the AE, severity, expectedness, relationship to study drug, duration (start/ stop date), action taken, and outcome. In addition, SAEs that meet the following definition are considered immediately reportable SAEs and will be reported to the NIH DSMB within **3 business days** of the site PI awareness of the event:

- All deaths and immediately life-threatening events, whether related or unrelated;
- SAEs that are unexpected and at least probably related;
- SAEs that are expected or unrelated, and are not deaths or immediately life threatening (i.e., suicide attempts), will be reported to the DSMB/NIMH in the tri-annual report.

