12 DISCONTINUATION AND REPLACEMENT OF SUBJECTS

12.1 Early Discontinuation of Study Drug

A subject may be discontinued from study treatment at any time if the subject, the investigator feels that it is not in the subject's best interest to continue. The following is a list of possible reasons for study treatment discontinuation:

- Subject withdrawal of consent
- Subject is not compliant with study procedures
- Adverse event that in the opinion of the investigator would be in the best interest of the subject to discontinue study treatment
- Lost to follow-up
- Need for early termination of study
- Positive pregnancy test (females)

If a subject is withdrawn from treatment due to an adverse event, the subject will be discontinued from the study. The site PI will follow up with the subject until the abnormal parameter or symptom has resolved or stabilized. All subjects who discontinue study treatment should come in for an early discontinuation visit as soon as possible. All subjects are free to withdraw from participation at any time, for any reason, specified or unspecified, and without prejudice. Reasonable attempts will be made by the investigator to provide a reason for subject withdrawals. The reason for the subject's withdrawal from the study will be specified in the subject's source documents. Refer to section 10.6 "Study exit Visit (Visit 6 – Day 57) and early withdrawal" for early termination procedures.

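### The SAP puts the end of adverse-event counting at eight weeks, but exit may fall at week 11–12, and the early-exit and 30-day rules do not line up with the scheduled contacts

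*SAP*

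**What the plan says.** **End of the AE window.** SAP section 4 counts events "that occur between randomization and study exit (V8) eight weeks after randomization will be determined". SAP 5.1 sums patient-time from randomization to study exit and sets no eight-week limit. SAP 5.5 starts the AE analysis at randomization and gives no end.

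**Visit windows.** Protocol section 10 places V5 after 7 to 14 days on the highest tolerated dose, and the footnote to Table 2 counts those two weeks from V4. For exit, section 10 refers to "V8 which may take place within six weeks of the Primary Outcome Visit (V5". Section 10.6 repeats the six-week limit. Sections 12.1 and 12.2 call the same visit Visit 6 and place it at Day 57. After screening, the ophthalmological exam and clinical laboratory tests are scheduled again only at exit. The protocol synopsis, protocol 4.1 and SAP 1.2.1 all give participation as up to 14 weeks.

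**Patients who stop early.** Under protocol 8.4.1, patients still intolerant after a dose reduction "will initiate the taper phase and will be exited early from the study protocol", with reference to 10.5 and 10.6. Section 12.1 says: "All subjects who discontinue study treatment should come in for an early discontinuation visit as soon as possible". Section 10.6 adds: "The subject will be considered exited from the study when all the procedures listed above will be completed". In 10.5, "The weekly phone calls will be scheduled one and two weeks after the Primary outcome visit (Visit 5), respectively". Section 10.3 exits patients stopped for QT findings only once their taper is complete.

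**30-day rules.** Section 11.2 makes reportable "Any death occurring within 30 days of the subject receiving study drug, regardless of the subject having discontinued from the protocol". Section 11.2.1 says that related AEs "continuing at 30 days post-last dose should have a comment in the source documents", and it treats pregnancies up to 30 days after study drug as expedited reports. No visit or call is scheduled after the exit visit.

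**The concern.** The sentence in SAP 4 names two end points, the exit visit and eight weeks, and treats them as the same date. Under the protocol's windows they need not be. A programmer could reasonably use either. If events stop at week 8 while person-time runs to exit, AE rates are understated, and eye and laboratory findings made at a late exit visit drop out of the count.

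Two gaps in follow-up add to this. The early-discontinuation passages can be read as closing out a patient who is still tapering, with no taper calls because those are timed from V5. The protocol names withdrawal seizures as a risk, so the taper is a period in which AE collection matters. The 30-day rules also assume knowledge of events that, for most taper schedules, no planned contact would obtain.

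**Working it through.** **1. The plan's own figures.** 5 weeks to V5 + 3 weeks of taper = 8 weeks (day 56), which matches the protocol's Day 57. Adding 6 weeks of screening: 6 + 5 + 3 = 14 weeks. Both stated figures reproduce, but only on the nominal schedule.

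**2. Latest permitted exit.** With V4 on day 28, V5 falls on day 35 to 42 (7 to 14 days later), and exit may be up to 42 days after V5.

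| V5 | Latest exit = V5 + 42 | Beyond day 56 |
|---|---|---|
| day 35 | day 77 (week 11) | 21 days |
| day 42 | day 84 (week 12) | 28 days |

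If V4 is itself three days late, as its window allows, the limit is 28 + 3 + 14 + 42 = day 87 (week 12.4). Dosing can also pass week 8: V5 on day 42 plus a 21-day taper ends on day 63, 7 days after day 56. Permitted participation is 6 + 12 = 18 weeks.

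**3. Effect on rates if the two end points are mixed.** For a constant event rate, with events counted to day 56 and person-time to exit, the reported rate divided by the true rate is 56 / exit day:

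- exit on day 77: 56/77 = 0.73
- exit on day 84: 56/84 = 0.67

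This applies only to patients who exit that late. A patient exiting on day 56 is unaffected.

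**4. Time from last dose to exit.** Last dose = V5 + taper length under 10.5, so the longest gap is 42 minus taper length.

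| Dose at V5 | Taper | Longest gap, last dose to exit | Against 30 days |
|---|---|---|---|
| 900 mg | 21 days | 42 − 21 = 21 days | 9 short |
| 750 mg | 14 days | 42 − 14 = 28 days | 2 short |
| 600 or 450 mg | 7 days | 42 − 7 = 35 days | can reach |
| 300 mg | none | 42 days | can reach |

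At the nominal Day 57 after a full taper (last dose day 35 + 21 = 56), the gap is about 0–1 day. A QT stop at V4 has its last dose on day 28 + 21 = 49. With the outcome visit on day 35, the latest exit is day 77, a gap of 28 days (2 short). These figures take the taper lengths of 10.5, and of 10.3 for QT stops, as written. Section 2.1 describes withdrawal over at least three weeks, which does not match the shorter schedules in 10.5; those passages must also be reconciled.

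**5. Early stoppers, passages side by side.**

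- 12.1 with 10.6: prompt visit, full exit list, exited when the list is complete. Nothing ties this to the end of the taper.
- 8.4.1: taper starts and the patient is exited early, under 10.5 and 10.6. The order is not stated.
- 10.5: calls are counted from V5, and the shorter tapers are defined by the dose at V5. A patient who stops before V5 has no anchor for either.
- 10.3: QT stops are exited after the taper.

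The protocol therefore has different exit rules for patients who taper early, and it does not say which governs AE collection.

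**The case against.** The strongest reply is that SAP 4 names study exit as the end point and gives eight weeks only as its usual date. Read with 5.1 and 5.5, events and person-time then both end at exit and nothing is lost. That reading is reasonable, perhaps the more natural one. A reader might infer that the SAP cuts off events at week 8 as a rule; the documents do not establish that. What stands is that the sentence supports both readings.

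A reader might also infer that early stoppers are exited while still tapering. The text permits this but does not prescribe it: 8.4.1 sends intolerant patients through the taper procedures, 10.3 exits QT stops only afterwards, and 10.6 lets exit procedures be spread over up to three days. The exposure at stake for intolerant patients is also limited. They have already had a dose reduction, so on 150 mg steps they are at 750 mg or less, for which 10.5 gives at most two weeks of taper. The unclear sequence stands.

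Nor is it true that no contact can reach day 30, since the one-week and no-taper cases allow it, although nothing requires an exit that late. The 30-day provisions are reporting duties rather than visit schedules. AEs present at exit and drug-related AEs are followed until resolved or stable, and patients are asked to report a pregnancy at once. That leaves new-onset events between exit and day 30, which no scheduled contact would find after the two longer tapers.

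**Conclusion.** The point holds as a set of inconsistencies to reconcile. SAP 4's eight weeks and the protocol's permitted exit differ by up to 3–4 weeks. If the figure is applied to events only, rates for the latest exits fall to 0.67–0.73 of their value, assuming a constant event rate. Stated participation is 14 weeks, against 18 permitted. Early stoppers may be exited before their taper ends. After the three-week and two-week tapers, the last scheduled contact falls at least 9 and 2 days short of day 30.

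A bias towards no difference between arms, from more early stopping on ezogabine, is tempting to infer but not shown. The 23% dizziness and 22% drowsiness figures are AE frequencies, not discontinuation rates; nobody discontinued in the pilot; and shorter follow-up also reduces person-time. Neither the size nor the direction of any bias can be computed from the documents. The link to the go decision is also unsettled: SAP 3.1 makes the primary endpoint the sole criterion, while the protocol also requires acceptable tolerability.

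**What to change.** - **SAP 4, 5.1 and 5.5:** state one AE end point, either actual exit or a fixed time after last dose, and use it for both events and person-time. Remove eight weeks as a definition. Section 5.5 should also say whether person-time enters the negative binomial model, since it names treatment group as the predictor and mentions no offset. This costs only SAP wording, to be settled before unblinding.
- **Protocol 8.4.1, 10.3, 10.5, 10.6 and 12.1:** reconcile these passages so that AE collection for early stoppers continues to the end of their taper, with contacts that do not depend on V5. This concerns data collection only; the dosing and taper rules are for the investigators to settle.
- **30-day rules in 11.2 and 11.2.1:** reconcile them with the last scheduled contact. One option is a single phone call per patient by existing staff, at most 48 calls.
- **Protocol synopsis, protocol 4.1 and SAP 1.2.1:** correct the 14-week figure to match the permitted windows, and use one visit number for exit (now Visit 6 in some places and V8 in others).

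The downside is a protocol amendment, which section 18.1 makes subject to IRB and DSMB approval, and a later last contact for some patients.
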